provided IPPI activity training videos (each 10-15 min), and be provided the IPPI manual with a checklist of steps, 60+ different IPPI protocols that address all 16 MDS 3.0 preferences in Section F, sample letters/scripts introducing the IPPI to family and staff, and communication tips sheets. Any member of the implementation team can deliver an IPPI activity. We will ask champion(s) to demonstrate an IPPI for care partners (e.g., CNAs) to watch, and then observe each care partner's initial IPPI implementation.

The champion(s) will be provided with a pragmatic data collection binder of paper forms (See Appendix A) to record these initial observations (in the form of a checklist). In addition, this binder will include a form to document staff training completion, resident preferences, and the behavior or mood item to target with the IPPI program that is most distressing to each identified eligible resident. Forms for champion(s) to document adverse events and withdraws will also be included in the binder.

Implementation team members will align stated preferences of each eligible resident with specific IPPI protocols (i.e., important preference for reading will be matched with a reading activity IPPI protocol). While any implementation team member can deliver an IPPI activity, we will encourage care partners to take the lead in implementation of the preferred IPPI activity with each enrolled resident on a regular basis. Initiation of engagement will be rolling, adding 3-7 residents per month for 3-4 consecutive months. The care partners will implement a minimum of 2 IPPI protocols per week with each resident for 6 months, to ensure continuous completion of the intervention through to the date of the resident's next two quarterly or annual MDS 3.0 assessment (3-month and 6-month follow-up data). The project manager will provide virtual coaching to communities throughout implementation as needed. Table 1 below outlines the intervention structure and implementation strategy. In addition, we identify the implementation measure/metric we will track during the course of implementation.

Table 1. IPPI Intervention Structure, Implementation Strategy, and Implementation Measures

Intervention Structure	Implementation Strategy	Implementation Measure
Establish Co-champions	Assess Organizational Readiness	Organizational Readiness for Implementing Change (ORIC) ³⁰

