The primary clinical outcome will be reports of distress as rated in the residents' MDS 3.0 annual or quarterly assessments in Section E and Section D (Saliba & Buchanan, 2009). These items will also be rated by the implementation team care partner delivering the intervention. These data will be collected at baseline (to determine eligibility) and at 3-months and 6-months post-intervention enrollment. The items in Section D and Section E are validated standardized items used to assess all NH residents in the United States receiving funding from the Centers for Medicare and Medicaid Services. Section D depression item responses are drawn from the widely used and validated PHQ-9 (Kroenke et al., 2001; anhedonia, sad mood, poor self-esteem, poor appetite, or restlessness). The items ask *“Over the past 2 weeks, have you been bothered by any of the following problems?”* and then if the resident responds “yes” they are asked *“About how often have you been bothered by this?”*. Item level scores are 0 (*did not occur*), 1 (2-6 days), 2 (7-11 days), or 3 (12-14 days). The Section E behavior items have been used as a valid indicator of behavioral distress (Saliba & Buchanan, 2009). Items include the presence of verbal, physical or other behavior symptoms directed toward others, rejection of care, and wandering. For section E, each behavior is rated with a 0 (*did not occur in the past week*), 1 (*occurred 1-3 days in the past week*), 2 (*occurred 4-6 days*) or 3 (*occurred daily*). For each resident care partners will have designated a targeted mood or behavior item selected for improvement and assessed via MDS data. The targeted mood or behavior selected by the care partner at baseline will be reassessed at 3-months and 6-months and recorded as 0 = *stayed the same as baseline* (e.g., score on MDS 3.0 baseline assessment equals score on MDS 3.0 follow-up assessment), 1 = *got better* (e.g., score on

MDS 3.0 baseline assessment is better (lower) than the score on the MDS 3.0 follow-up assessment), or 2 = *got worse* (e.g., score on MDS 3.0 baseline assessment is worse (higher) than the score on MDS 3.0 follow-up assessment) for our primary, person-centered clinical outcome. The type of mood or behavior item being tracked will be different for each resident (e.g., wandering for one, verbal behavior for another)

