9.4.1 Primary outcome

The primary clinical outcome will be reports of distress as rated in the residents' MDS 3.0 annual or quarterly assessments in Section E and Section D (Saliba & Buchanan, 2009). These items will also be rated by the implementation team care partner delivering the intervention. These data will be collected at baseline (to determine eligibility) and at 3-months and 6-months post-intervention enrollment. For each resident, a targeted mood or behavior item selected for improvement and assessed via MDS data will be used as the primary outcome. The targeted mood or behavior will be recorded as 0 = *stayed the same as baseline* (e.g., score on MDS 3.0 baseline assessment equals score on MDS 3.0 follow-up assessment), 1 = *got better* (e.g., score on MDS 3.0 baseline assessment is better (lower) than the score on the MDS 3.0 follow-up assessment), or 2 = *got worse* (e.g., score on MDS 3.0 baseline assessment is worse (higher) than the score on MDS 3.0 follow-up assessment) for our primary, person-centered clinical outcome at 3-months and 6-months post

intervention enrollment. The type of mood or behavior item being tracked will be different for each resident (e.g., wandering for one, verbal behavior for another).

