9.5 Data Analyses

Analysis of data will be descriptive. To address our first objective of clinical impact for residents, we will code a change score for each enrolled resident's targeted behaviors (e.g., improved, stayed same, worsened) in two ways. We will use the MDS 3.0 data between baseline and 6 months. We will report aggregate percentages of improved, stayed same, and worsened from the MDS 3.0 data. For implementation team members, the outcomes of knowledge and self-efficacy will be analyzed through paired samples t-tests of pre- and post-EFCT test measures.

For our second objective of feasibility and fidelity, we will calculate the number of residents each NH is able to engage as a percentage of the goal (e.g., 15 residents minimum) via data collected from the Resident Preferences Worksheet. We will also calculate the percentage of the implementation team that completed the EFCT based on data from the EFCT LMS. Finally, we will calculate the average number of IPPIs completed (via the EMR). Acceptability, feasibility, and appropriateness will be calculated according to responses from the exit interview (Weiner et al., 2017; AIM, IAM, and FIM measures). Qualitative data collected by the semi-structured exit interview

will be audio recorded, transcribed verbatim, and coded for facilitators and barriers in Dedoose.

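### A target item at the top score of 3 at baseline cannot be recorded as worse, and Section 9.5 shows nothing by baseline score, so stability cannot be told from ceiling

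*Combined protocol and SAP*

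**What the plan says.** Section 9.5 states that "we will code a change score for each enrolled resident's targeted behaviors", in three categories (improved, same, worsened), and then: "We will report aggregate percentages of improved, stayed same, and worsened from the MDS 3.0 data". Section 9.4.1 makes this change in the target item the primary clinical outcome, at 3 and 6 months. Section 9.1 describes a single-group, within-person design.

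Section 9.1 also gives the scales. "For section E, each behavior is rated with a 0" if it did not occur in the past week, rising to 3 if it occurred daily. Section D items score 0 if the problem did not occur, and otherwise "1 (2-6 days), 2 (7-11 days), or 3 (12-14 days". Both scales stop at 3.

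The inclusion criteria in Section 4 require a non-zero response on at least one qualifying item and set no upper limit. Section 3 describes the target as "the behavior or mood item to target with the IPPI program that is most distressing to each identified eligible resident".

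The coding rule in Section 9.4.1 assigns *got better* when the "score on MDS 3.0 baseline assessment is better (lower) than the score on the MDS 3.0 follow-up assessment", and *got worse* when the "score on MDS 3.0 baseline assessment is worse (higher) than the score on MDS 3.0 follow-up assessment". The same wording appears in Section 9.1 and at both follow-ups in Section 6.2.3.

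**The concern.** On a 0-3 item, a score of 3 leaves no room to rise. If worsening means a higher score, a resident who starts at 3 has only two possible outcomes, improved or same. A resident at 1 or 2 has all three. The pooled table mixes these groups, and nothing in Section 9.5 shows how many residents are in each.

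Two things follow. A resident who stays at 3 throughout is counted as unchanged alongside one who stays at 1, so the same category mixes true stability with residents for whom worsening could not be recorded. And the percentage worsened is lower than the rate among residents in whom a rise was possible.

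The design has no comparison group in which the same ceiling would appear. No test or model is planned for the resident outcome, so these percentages are its whole quantitative result. Section 9.2 says that the findings will inform the approach and power of a full-scale trial. A pooled rate that depends on the baseline mix carries over poorly to a sample with a different mix.

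**Working it through.** **Step 1: possible codes.** Take every baseline and follow-up pair on the 0-3 scale, once with the labels in their plain sense (lower is better) and once with the parenthetical rule applied literally.

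| Baseline | Possible codes, plain labels | Possible codes, literal rule |
|---|---|---|
| 0 | same, worse | same, better |
| 1 | better, same, worse | better, same, worse |
| 2 | better, same, worse | better, same, worse |
| 3 | better, same | same, worse |

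From a baseline of 3, a follow-up of 0, 1 or 2 is *better* under the plain labels and *worse* under the literal rule. The literal rule swaps the two codes for every resident who changes. The plain sense is evidently intended: the rule itself glosses better as lower and worse as higher, and Section 1.1 hypothesizes decreased distress. The rest of the working uses the plain sense.

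**Step 2: effect on the pooled percentage.** The plan states no expected percentage worsened, so there is no figure to reproduce. Let q be the share of residents whose target is at 3 at baseline, and w the share of those below 3 who worsen. The documents give neither, so both are assumed over a range.

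- Pooled percentage worsened = w × (1 − q)
- Percentage worsened among those below 3 = w
- Gap = w − w × (1 − q) = w × q

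| w | q = 0% | q = 10% | q = 20% | q = 30% | q = 50% |
|---|---|---|---|---|---|
| 10% | 10% | 9% | 8% | 7% | 5% |
| 20% | 20% | 18% | 16% | 14% | 10% |
| 30% | 30% | 27% | 24% | 21% | 15% |

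Cells are pooled percentages worsened. The gap is w minus the cell: none at q = 0, and from 1 point (w = 10%, q = 10%) to 15 points (w = 30%, q = 50%).

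**Step 3: in counts.** Take the 108 residents in the précis, w = 20% and q = 30%. Residents below 3: 108 × 0.70 = 75.6. Worsened: 75.6 × 0.20 = 15.1. Pooled: 15.1/108 = 14%. Among those able to worsen: 15.1/75.6 = 20%.

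**Step 4: against sampling error.** For a proportion of 20% in 108 residents, the 95% half-width is 1.96 × √(0.20 × 0.80/108) = 7.5 points. The 6-point gap in Step 3 is of similar order. Unlike sampling error, it does not shrink as the sample grows.

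**The case against.** The case against has several parts.

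*The written rule says the opposite.* Read literally, a baseline of 3 can be coded worse and cannot be coded better. This stands as a separate and larger defect, because it affects everyone who changes. It does not remove the boundary problem, since under either reading one change category is closed to residents at 3.

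*The pooled percentage is not wrong.* A reader might infer that the reported figure is biased low by design. The documents do not support that. As the share of all enrolled residents with a recorded rise, it is correct. It is low only as a rate among those who could rise, which the plan never says it is estimating. The analysis is descriptive, and no test or decision threshold depends on it.

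*Targets need not cluster at 3.* A reader might take the choice of the most distressing item to mean the most frequent one. Section 3 does not say so; a rare outburst may be the most distressing. Nor do the documents require the target to be the item that triggered entry. A target at 0, which can only stay or worsen, is therefore not excluded.

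*Hidden harm is limited.* A reader might infer that any deterioration from 3 disappears. For Section E, 3 already means daily, so no higher frequency exists. For Section D, only movement within 12-14 days is lost, and loss within a band also occurs at scores 1 and 2. Section 7.3 separately captures extreme distress as an adverse event.

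*The denominator is inferred.* Section 9.5 refers to each enrolled resident but states no denominator, and Section 8 anticipates withdrawals and deaths. That is a reason to state the denominator.

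**Conclusion.** The point holds in a limited form. On the evident meaning of the labels, a target at 3 at baseline cannot be coded worse, while any target above 0 can be coded better. Section 9.5 offers no breakdown that would let a reader see how much of the unchanged group is ceiling. The pooled percentages remain valid as shares of all enrolled residents, but they understate worsening among residents who could worsen.

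The size is unknown. The 1 to 15 point range rests wholly on assumed values of w and q, and the gap is zero if nobody starts at 3. This is an inexpensive improvement to the reporting of the primary resident outcome. It does not show that the planned percentages are invalid, and it comes after correction of the coding direction.

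**What to change.** 1. Reconcile the parenthetical rules with their labels wherever they occur (Sections 6.2.3, 9.1 and 9.4.1), so that the direction of coding is stated once and consistently.
2. In Section 9.5, keep the pooled three-category percentages and state their denominator.
3. Add, at 3 and at 6 months, the 4×4 table of baseline by follow-up score for the target item, or the three categories by baseline score. Give the number of residents at baseline 3, and at 0 if any.
4. Report the percentage worsened among residents with a baseline below 3 as a supplementary figure only. If it replaced the pooled figure, the three categories would sit on different denominators and no longer sum to 100%.

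The data are MDS scores that the study already receives, so no new collection is needed. The cost is one extra table with small cell counts.

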Subject Identification	Identify residents who score 0-12 on the BIMS with either a non-zero score on one of 5 Section D Mood items or a non-zero score on Section E Behaviors from MDS 3.0 upon completion of a scheduled annual or quarterly MDS 3.0 assessment.	That 15-20 residents with both of these criteria are engaged during the pilot timeframe per NH community - approximately 3-8 residents per month
Implementation team identified	Recommended Activity Director and DON, and CNAs or activity personnel who care for residents identified	That 3-5 staff volunteer from each community to lead and deliver IPPI activities
Orientation to IPPI	Virtual Coaching session	Does champion/team attend orientation Yes/No measured by Project Director
Emotion-Focused Communication Training	Recommended champion(s) and care partners (e.g., CNAs/Activity personnel) complete on-line, self-paced, interactive education session prior to initiating implementation	That all of the identified implementation team completes training as identified in the learning management system
Learn how to conduct an IPPI protocol	Watch IPPI training videos, review tip sheets on considerations before, during, and ending an IPPI	Binder for champion to record if activity was completed or not
Match Resident Preferences with IPPI protocols	Review Section F of MDS 3.0 to identify resident important preferences and review IPPI Protocols on website Identify 1-2 protocols for use with resident	Completion of the Resident Preference Worksheet and EMR

Intervention Structure	Implementation Strategy	Implementation Measure
Care Conference Discussion	Identify targeted behavior to be addressed with IPPI and who will be the primary IPPI delivery care partner	Obtain a deidentified print out of the care plan and look for documentation of targeted behavior and care partner
Identify and procure IPPI supplies needed	Managing supplies – what is needed, where will they be stored, identified	Exit interview and Resident Preferences Worksheet
Assess Fidelity to IPPI protocol	Champion does one IPPI with each resident while care partner watches, then champion watches while care partner conducts one and documents if IPPI steps followed	Observation by champion is documented with the Pragmatic Checklist
Assess Adherence to IPPI protocol and participant responsiveness	Conduct two 10 min IPPIs per week over the course of 6 months (e.g., 48 sessions total)	Documentation of each of 48 IPPIs completed for each resident in EMR

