5.3 Adherence Assessment

Adherence to the study regimen is defined as completion of at least 80% of designated IPPI sessions per eligible/enrolled resident. Adherence to completion of two 10-minute IPPIs per week over the course of 6-months (e.g., 48 sessions total) will be tracked in the UCH EMR upon completion of each IPPI activity with each resident (see evaluations section below).

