6.1 Schedule of Evaluations

Assessment	Pre-enrollment	Baseline, Enrollment (Day 0)	Each IPPI (2x a week for 180 days)	3-month Assessment (~Day 90)	6-month Assessment (~Day 180)	Post Intervention Trial
Organizational Readiness for Implementing Change (ORIC)	X					
MDS 3.0 data of residents BIMS scores and Section D and E Responses (rolling ; each resident assessed for enrollment to serve as baseline assessment, 3-mon, and 6-mon)	X	X		X	X	
Identify Implementation team (Y/N)	X					
Virtual Coaching session attendance (Y/N)	X			X	X	
Emotion-Focused Communication Training (EFCT) completion (Y/N)	X					
Emotion-Focused Communication Training (EFCT) pre and post-test (knowledge, efficacy)	X					
IPPI Training (watching 2 videos) completed (Y/N)	X					
Resident Preferences Worksheet (rolling)		X	X	X	X	
Care Plan Documentation (Y/N)		X	X	X	X	

Fidelity Assessment with Pragmatic Checklist (observation of 1st IPPI between each resident and implementation team member delivering IPPI)			X (1 st IPPI only)			
Exit Interview (communication, acceptability, feasibility, appropriateness, facilitators, and barriers)						X
Troubleshooting (count of contacts)	X	X	X	X	X	
Intervention Withdrawal form			X			
Adverse Events form			X			

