6.2.3 Follow-up Visits

- IPPI completions 2x weekly:
 - The Fidelity Assessment with Pragmatic Checklist will be completed the first time a member of the intervention team completes an IPPI with a resident. This will be completed by the site champion when shadowing the care partner in implementation.
 - IPPIs will be documented in the UCH EMR through Point-Click-Care.
 - During implementation, troubleshooting (count of contacts of the implementation teams with the PI/Project team) will be recorded.
 - If an eligible resident is withdrawn from participation, the withdrawal date, and the reason will be documented on an Intervention Withdrawal form and provided to the project PI. This form is part of the binder that will be provided to each site champion(s).
 - Adverse Events will be reported directly to the PI if they occur as per section 7.3 below.
- 3-months (~90 days):
 - Distress data (Section E and Section D) from the next completed MDS 3.0 assessment (annual or quarterly) will be provided to the PI by the UCH IT Corporate office. The Centers for Medicare and Medicaid Services require completion of an assessment every 3-months; however, experience indicates that there is individual variability in actual completion times and therefore we will not enforce a strict allowable time window for these data. Change in each Section E/Section D item will be scored as 0 = *stayed the same as baseline* (e.g., score on MDS 3.0 baseline assessment equals score on MDS 3.0 follow-up assessment), 1 = *got better* (e.g., score on MDS 3.0 baseline assessment is better (lower) than the score on the MDS 3.0 follow-up assessment), or 2 = *got worse* (e.g., score on MDS 3.0 baseline assessment is worse (higher) than the score on MDS 3.0 follow-up assessment) for our primary, person-centered clinical outcome.
- 6-months (~180 days):
 - Distress data (Section E and Section D) from the next completed MDS 3.0 assessment (annual or quarterly ~6-months post baseline assessment) will be provided to the PI by the UCH IT Corporate office. The Centers for Medicare and Medicaid Services require completion of an assessment every 3-months; however, experience indicates that there is individual variability in actual completion times and therefore will not enforce a

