8 INTERVENTION DISCONTINUATION

Participating in the IPPI intervention is optional for residents. Residents can refuse participation at any time. The staff can choose to discontinue the IPPI with any participant based upon their clinical judgement and the individual may be withdrawn from the study.

Withdrawal can also follow a significant health change or hospitalization that makes the participant unable to continue to participate in the IPPI intervention activities. Implementation team clinical staff will make a judgement call.

Participants may also be withdrawn due to death. Residents living with dementia in a NH are a vulnerable population, health events are common and anticipated (i.e. falls).

Participants may also be withdrawn from the study if the individual leaves the NH to move to another NH. The resident must continue to reside in the same NH for the 6-months of the study period to be engaged in the intervention.

For all reasons of withdrawal, the implementation team for a given resident will communicate the withdrawal to the PI with the second to last column on the Resident Preferences Worksheet stating the date and the reason.

While there is no formal plan for replacement of subjects, due the rolling nature of enrollment, additional eligible residents may be added to the study to accommodate a withdrawal if it occurs within the first 3 consecutive months of the study.

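### Delivery and adherence have no defined denominator for residents who die, transfer or are absent; sessions per available resident-week should be reported beside the mean count

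*Combined protocol and SAP*

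**What the plan says.** The delivery summary in Section 9.5 (Data Analyses) is a count: "Finally, we will calculate the average number of IPPIs completed (via the EMR"). It names no denominator, no period at risk and no analysis set.

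Section 5.3 (Adherence Assessment) states: "Adherence to the study regimen is defined as completion of at least 80% of designated IPPI sessions per eligible/enrolled resident". It then describes what is tracked: "Adherence to completion of two 10-minute IPPIs per week over the course of 6-months (e.g., 48 sessions total"). Table 1 in Section 3 gives the corresponding measure as "Documentation of each of 48 IPPIs completed for each resident in EMR".

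The length of the course is described in other ways too. The Schedule of Evaluations (Section 6.1) has "Each IPPI (2x a week for 180 days"), and Section 3 says "The care partners will implement a minimum of 2 IPPI protocols per week with each resident for 6 months".

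The protocol expects early exits. Section 7 anticipates falls, hospital visits and deaths because of age and illness. Section 8 lists death, transfer, hospitalization and health change as grounds for withdrawal, and adds: "The resident must continue to reside in the same NH for the 6-months of the study period to be engaged in the intervention". Under Section 6.2.3, "the withdrawal date, and the reason will be documented on an Intervention Withdrawal form".

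Sections 9.1 and 9.4.2 also promise to report how much, how often and for how long sessions were delivered, so as to judge whether two a week was achieved. Session dates are recorded in the EMR. Section 9.5 gives no calculation for how often.

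**The concern.** The pilot's delivery question is about a rate: can homes give two sessions a week to the residents in front of them? A mean count per resident, or a percentage of a fixed total, answers that question only if everyone is present for the same length of time. In this population they will not be.

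Two residents show the problem. One leaves at week 12 having received all 24 sessions then due. The other is present for 24 weeks and receives one a week. Both have 24 sessions and both score 24/48 = 50%, but the first home delivered fully and the second delivered half.

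Section 9.2 says the findings will guide adaptations for a full-scale trial, and Section 11.3 promises each home its own report. A home with frailer residents could look like a weaker implementer, and the plan has no figure that would show otherwise. The choice between counting leavers and dropping them would also be made after the data are seen.

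**Working it through.** **Inputs from the protocol.** Two sessions a week; total 48; threshold 80% (Section 5.3). Delivery period 180 days (Section 6.1). Resident number 108 (Précis), used for illustration only. No attrition rate is stated, so the share leaving, q, is an assumption, shown from 5% to 30%. Exits are assumed to be spread evenly over the course.

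**The plan's own figure.** 2 × 24 weeks = 48, which reproduces the stated total. Two a week for 180 days is 2 × 180/7 = 51.4, and for 26 weeks it is 52; neither gives 48.

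**Threshold.** 0.80 × 48 = 38.4, so 39 sessions. At two a week this takes 39/2 = 19.5 weeks (about 137 days). A resident who leaves earlier cannot be adherent against 48, however good the delivery. For a temporary absence, 4 weeks of 24 leaves 40/48 = 83.3% (passes), and 5 weeks leaves 38/48 = 79.2% (fails).

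**All enrolled residents counted against 48, full delivery while present.** A leaver is present for half the course on average, so the mean is 48 × (1 − q/2). The share reaching 39 is (1 − q) + q × (1 − 39/48).

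| Assumed q | Mean sessions | Mean / 48 | Share reaching 39 | Of 108 | Sessions per available week |
|---|---|---|---|---|---|
| 5% | 46.8 | 97.5% | 95.9% | 104 | 2.0 |
| 10% | 45.6 | 95.0% | 91.9% | 99 | 2.0 |
| 20% | 43.2 | 90.0% | 83.8% | 90 | 2.0 |
| 30% | 40.8 | 85.0% | 75.6% | 82 | 2.0 |

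Delivery is identical in every row; only attrition changes. With 90% delivery and q = 20%, the mean is 48 × 0.9 × 0.9 = 38.9. That is 38.9/24 = 1.62 a week over the nominal course, against 2 × 0.9 = 1.80 per available week.

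**Leavers dropped.** With full delivery the mean is 48 whatever q is, but it describes only the stayers: at q = 20%, 0.8 × 108, or about 86 of 108.

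**Effect of 48 against 180 days.** For a resident who stays 180 days, 48 sessions is 48/51.4 = 93.3% of two a week but scores 100%. The 39-session threshold is 39/51.4 = 75.8% of it but scores adherent. With full delivery over 180 days, the mean divided by 48 is 51.4 × (1 − q/2)/48:

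- q = 10%: 48.9/48 = 101.8%
- q = 20%: 46.3/48 = 96.4%
- q = 30%: 43.7/48 = 91.1%

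It passes through 100% when 1 − 48/51.4 = 6.7% of resident-time is lost, which is q of about 13%. Below that, the ratio to 48 overstates delivery; above it, the ratio understates delivery.

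**The case against.** A reader might infer that the plan scores time after death or transfer as missed sessions, and so must understate delivery. The documents do not support that, for two reasons.

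First, the mean count has no denominator, so it scores nothing as missed. The adherence rule refers to *designated* sessions and introduces 48 only as an example. Whether sessions remain designated after withdrawal is not stated. Counting every enrolled resident against 48 is the natural reading of Section 5.3 with Table 1, but it is not the only one. If leavers are dropped, this downward effect does not arise.

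Second, the sign is not fixed. As shown above, a base of 48 against 180 days of delivery can push the ratio over 100% at low attrition, and Section 3 describes two a week as a minimum.

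It is also fair to say that delivery is not left wholly to the mean count. Frequency is a listed outcome in Sections 9.1 and 9.4.2, and it is the right kind of measure. What it lacks is a formula and a time base.

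Mean sessions per enrolled resident, leavers included, is a legitimate measure of dose received and is useful for planning a trial in the same population. It should stay. No progression rule depends on adherence and the analysis is descriptive, which limits the harm.

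Lastly, a rate per available week needs rules for refusal, for staff stopping the sessions and for health-related stops. Not all the data are assured. Section 8 says the worksheet column will state the date and reason, but the column in Appendix A asks only whether the resident completed and, if not, why. Neither Section 6.2.1 nor Section 10.2 lists hospital days in the data extract.

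**Conclusion.** The point holds as an undefined denominator with a cheap and better alternative, not as a demonstrated bias. On the natural reading of Section 5.3 and Table 1, a resident who leaves before about 19.5 weeks is non-adherent despite full delivery, and the mean count falls by q/2. On the other reading, the result describes stayers only. Neither separates how well homes deliver from how long residents remain.

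The sizes (5% to 15% off the mean for q of 10% to 30%) rest on assumed attrition, even exit times and constant delivery while present. The protocol supplies none of these. A claim that the reported ratio to 48 will be too low overall is not supported until 48 sessions and two a week for 180 days are reconciled. Sessions per available week avoids that dispute over the total, though the end of the 6-month course still needs one definition. This is an improvement worth making before analysis; it does not undermine the study.

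**What to change.** - **Section 9.5:** define frequency as total sessions completed divided by total available resident-weeks, overall and by home. Available time runs from the first IPPI to the earliest of death, transfer out or the end of the 6-month course. Show the raw mean per enrolled resident beside it. Residents enrolled but never started count as zero in that mean and should be listed, because the rate gives them no start date.
- **Section 5.3:** report the share reaching 80% of 2 × available weeks beside the share reaching 80% of the fixed total.
- **Classification of stops:** keep time after a resident's refusal or a staff-initiated stop in the denominator, so the rate cannot hide non-delivery. Report stops for a health change separately, by recorded reason.
- **Data:** add the withdrawal date to the Appendix A worksheet column. Subtract hospital days only if the EMR extract contains them.
- **Consistency:** reconcile the 48-session total with the 180-day schedule, so that the fixed total and the end of the course agree.

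The cost is a few sentences, one extra column in the report and a short classification of withdrawal reasons. Session dates are already recorded, and withdrawal dates are already promised in Section 6.2.3. Treatment of residents does not change.
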